Loss of privacy: Every effort will be made to protect the subject's privacy and information will be handled in a confidential manner. The only information that will be provided with the subject's stored blood and urine samples is a study code. Files that link the subjects name to the code number will be kept in a locked cabinet and only the study staff will have access to them. The samples will be provided to the researchers in such a manner whereby it will not be possible for them to connect the subject's identity with the sample or medical information. Information about race, ethnicity, sex and medical history may be made available to the investigators studying the blood, muscle tissue and urine samples. Such information might be important for research. Although no one can absolutely guarantee confidentiality, using a code number greatly reduces the chance that someone will ever be able to link the subjects name to their sample or to their results.

Confidentiality: All records pertaining to the subject's involvement in this research study will be stored in locked file cabinets. Only a subject number in these records will identify him or her. Any information about the subject or his or her treatment will be handled in a confidential manner consistent with other identifiable health information. The subject will not be specifically identified in any publication of research results.

Potential benefits: There may be no direct benefit to participate in this study. There is no guarantee that participants will receive any personal benefit from participating. It is hoped that the information gained from the study will be beneficial to patients in the future.

Alternative Treatments: Other treatments available to patients include other immunosuppressive medications known to be considered as possibly effective in patients with immunological diseases. These drugs may be effective in managing the symptoms associated with JDM. The Principal Investigator or Associate Investigators will discuss all of the treatment options with potential participants.

Evaluation of Risk/Benefit Ratio: If abatacept proves to be effective, many such patients with JDM may ultimately benefit from this therapy. Such benefits may include improved symptoms and health. Practitioners may gain increased knowledge and treatment of myositis in clinical practice. Subjects participating in this study may experience some benefit during the period of study medication therapy. Evaluation is performed as per the statistical information provided in the protocol. The risks for those subjects involved in this study are reasonable when compared to the potential

disease damage and catastrophic sequelae that occurs in adult and pediatric patients with inflammatory myopathy.

Reproductive Risks: Animal studies to determine the effects of the study drug on the fetus have not been done. To avoid risk to the fetus, it is important that female participants or female partners of male participants take care to avoid becoming pregnant during this study. Avoiding sexual activity is the only certain method to prevent pregnancy. However, females of child-bearing potential must be willing to use an appropriate method of birth control (such as female use of a diaphragm, intrauterine device (IUD), or contraceptive sponge, in addition to male use of a condom) or the female should be using prescribed “birth control” pills, injections, or implants throughout the study. Even with use of these birth control measures, pregnancy could still result. The risks of receiving the study drug while pregnant include potential loss of pregnancy or possible birth defects. Females of child-bearing potential will undergo a urine pregnancy test prior to exposure to the study drug. In the pediatric group the parent signing the consent will be informed of the result of the pregnancy test.

1.4 ETHICAL CONSIDERATIONS

Good Clinical Practice

This study will be conducted in accordance with Good Clinical Practice (GCP), as defined by the International Conference on Harmonization (ICH) and in accordance with the ethical principles underlying European Union Directive 2001/20/EC and the United States Code of Federal Regulations, Title 21, Part 50 (21CFR50).

The study will be conducted in compliance with the protocol. The protocol, any amendments, and the subject informed consent will receive Institutional Review Board/Independent Ethics Committee (IRB/IEC) approval/favorable opinion before initiation of the study.

All potential serious breaches will be reported to Bristol-Myers Squibb (BMS) immediately. A serious breach is a breach of the conditions and principles of GCP in connection with the study or the protocol, which is likely to affect, to a significant degree, the safety or physical or mental integrity of the subjects of the study or the scientific value of the study.

Study personnel involved in conducting this study will be qualified by education, training, and experience to perform their respective tasks. This study will not use the services of study personnel where sanctions have been invoked or where there has been scientific misconduct or fraud (e.g., loss of medical licensure; debarment).

1.5 RATIONALE

JDM is an autoimmune disease involving specific immunity, including plasmacytoid dendritic cells, B and CD4+ T lymphocytes. We postulate that the immunomodulatory action of abatacept in JDM will inhibit the co-stimulatory signal from CD80 and CD86, by inhibiting dendritic-cell mediated T cell activation. Our hypothesis is that treatment refractory patients with JDM will respond to abatacept and that abatacept will also be safe for use in this population.

2.0 OBJECTIVES

This open label non-randomized trial will assess the safety and efficacy of subcutaneous abatacept in 10 patients ≥ 7 years of age with refractory JDM.

2.1 PRIMARY OBJECTIVE

AIM: To assess the safety and efficacy of subcutaneous abatacept in an open-label trial of refractory JDM in 10 adults and children.

- **Hypothesis A: *Abatacept will be well-tolerated and safe in treatment–refractory JDM patients.*** For this, the NCI Common Terminology criteria version 4.0 June 2010 will be applied. Medical records will be reviewed for the 6 months prior to enrollment to obtain adverse events prior to beginning abatacept, which will be compared to any adverse events that develop after abatacept was initiated. Particular attention will be given to serious adverse events and infections. Patient evaluations will include: vital sign measurement, physical examination, and laboratory parameters for hematology and routine chemistries.
- **Hypothesis B: *Patients will clinically improve after treatment with abatacept.*** We hypothesize that at least 6 of 10 patients will meet the myositis preliminary definition of improvement after receiving 24 weeks of therapy with abatacept.

Definitions of improvement (DOIs) for clinical trials in IIM have recently been proposed by the IMACS Group (International Myositis Assessment and Clinical Studies) for adult and pediatric myositis utilizing six core set measures among five domains of myositis disease activity (38) (**see Appendix C**). They are:

- a) Physician global disease activity;
- b) Parent/patient global disease activity;
- c) Muscle strength, utilizing manual muscle strength testing (MMT8);
- d) Physical function assessment using the (Childhood) Health Assessment Questionnaire (CHAQ);
- e) Laboratory assessment using the most abnormal serum muscle enzyme level; and
- f) Extra-muscular disease activity using the Myositis Disease Activity Assessment Tool (MDAAT). (see section 14.0: assessment tools: description) (39)

For this clinical trial, the primary endpoint will be the published Definition of Improvement (DOI): 3 of any of the 6 core set measures improved by $\geq 20\%$, with no more than 2 of the core set measures worsening by $\geq 25\%$ (worsening measures cannot include the muscle strength). (Appendix D1) (38)

The PRINTO Group (Pediatric Rheumatology International Trials Organization) has developed and validated a core set of outcome variables for the evaluation of response to therapy in JDM. (40) (Appendix C)

The additional PRINTO core set activity measures are:

- 1) Childhood Myositis Assessment Scale is used as a measure of strength;
- 2) A health related quality of life measure, CHQ-PF50, is used and
- 3) Disease Activity Score (DAS) is used as a measure of global activity (42)

PRINTO also has a definition of minimal clinical improvement (20%), moderate (50%) and major (70%) improvement (41) (Appendix D).

PRINTO has also defined clinically inactive disease (41) as creatine kinase ≤ 150 (within normal limits), CMAS ≥ 48 , MMT ≥ 78 and Physician Global Activity VAS ≤ 0.2 . (41) (Appendix D)

The frequency of minimal, moderate and major improvement by the DOIs, with 20%, 50% and 70% change, as well as clinically inactive disease by the PRINTO criteria will also be examined in this trial.

Finally, the DOIs are currently undergoing revision in an ACR-EULAR project that is combining the efforts of IMACS and PRINTO. New definitions of minimal, moderate and major improvement have been developed and are expected to be finalized within the coming year. These newly-developed definitions will be added to the criteria as a secondary efficacy outcome measures for this trial (**Appendix D2**). Other criteria found to perform very highly in the ACR-EULAR project will be used as secondary endpoints in this trial (Appendix D2).

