3.0 STUDY DESIGN

TREATMENT PHASE

This study will employ an open label nonrandomized design in the treatment of subjects with JDM. Study participation will consist of a screening visit and 5 protocol visits over six months (week 0, week 6, week 12, week 18, and week 24) for each subject, and phone follow-up in between in-person visits (week 2, week 4, week 8, week 10, week 14, week 16, week 20, and week 22). Some patients will undergo some of the screening tests at home, and present results at a screening visit. This will enable them to move to the week 0 visit simultaneously and begin treatment.

At Visit 1, which will be treatment initiation, eligible subjects will be instructed on the use and side effects of subcutaneous abatacept. Patients will be started on the study drug (abatacept) 125 mg SQ weekly for subjects with body weight \geq 50KG and 87.5 mg SQ for subjects with weight <50 KG. For patients not improving with therapy by at least 5% on

at least 3 of 6 core set measures (IMACS or PRINTO measures) at week 12, they would be offered the opportunity to increase their dose of treatment to abatacept 212.5 mg SQ weekly (125 mg prefilled syringe plus 87.5 mg prefilled syringe) for subjects with weight \geq 50KG and 137.5 mg SQ weekly (87.5 mg prefilled syringe plus 50 mg prefilled syringe) for subjects with weight <50KG, or to continue on their present dose.

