3.2 SAFETY ENDPOINTS

Safety assessment will include adverse events, vital signs, physical examination findings, laboratory parameters and NCI common terminology safety assessment, including focus on serious adverse events and the infection module. This will be collected in person during study visits, but in between study visits, a phone call will be made at weeks 2, 4,8,10,14,16, 20 and 22 to review adverse events.

Patient evaluations include:

1. Vital sign measurement, physical examination

2. Laboratory parameters for hematology, routine chemistry, muscle enzymes and urinalysis
3. NCI Common Toxicity assessment (version 4.0 June 2010) including focus on serious adverse events and the infection module.
4. Adverse event monitoring
5. Assessment of primary and secondary efficacy endpoints

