9	Known or suspected history of drug or alcohol abuse within the past 6 months as determined by the medical record or patient interview
10	Anticipated poor compliance
11	Participation in another clinical experimental therapeutic study within 30 days of screening visit.
12	Any history or evidence of severe illness or any other condition that would make the patient, in the opinion of the investigator unsuitable for the study.
13	Low total WBC <2.000, platelets ≤ 100,000/mm ³ ; hemoglobin ≤10 gm/dl

14	History of recurrent infection including active skin infections with calcinosis
15	
Is the patient receiving and concomitant treatment with anti-TNF therapies, rituximab or anakinra or other biologic therapies?
 
Washout period for etanercept is 1 month and anakinra is 1 week Washout period for adalimumab and infliximab is 2 months Washout period for Rituximab is 3 and CD19 has to be detectable and IgG level is within normal limits (normal serum levels of IgG per reference lab: 7-9 years ≥ 572 mg/dl, 10-11 yrs ≥ 698 mg/dl, 12-13 yrs ≥ 759 mg/dl, 14-15 yrs ≥ 716 mg/dl, 16-19 yrs ≥ 549 mg/dl, >19 yrs ≥ 700 mg/dl).

16	Initiation of colchicine and hydroxychloroquine as new drugs during study participation is not allowed.
17	Initiation of statins or fibric acid derivatives during study participation is not allowed.
18	Initiation of an exercise program within 4 weeks of the screening visit. Only a stretching program may be initiated during the study
19	Prisoners or subjects who are involuntarily incarcerated.
20	Subjects who are compulsorily detained for treatment of either a psychiatric or physical (e.g., infectious disease) illness

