- Collect pre -treatment research blood samples for Immunophenotyping (T, B cells and macrophages), gene expression, and cytokine/chemokine analysis (see Section 3.1.h)
- Myositis specific and associated autoantibody testing
- Collect pre -treatment blood samples for immunogenicity
- Pregnancy test for females of child bearing potential (where applicable)
- Administer first dose of study medication and observe after the injection for at least 15 minutes
- Schedule and instruct the subject to return for the next visit, teaching injection technique, review medication administration log.

Phone follow-up #1 (14 days (+/- 7 days after visit 1)

- Adverse events will be reviewed and recorded (NCI Common Toxicity criteria version 4.0).

Phone follow-up #2 (will occur 28 days (+/- 7 days) after visit 1.

- Adverse events will be reviewed and recorded.

Visit 2 (week 6) will occur 42 days (+/-10 days) after visit 1

- Review concomitant medication and query for adverse events and document in CRF
- NCI Common Toxicity Assessment
- Obtain vital signs (HR, BP, RR, oral temperature and weight) and if indicated, by history of shortness of breath or lung disease, pulse oximetry)
- Medical history and perform a full physical examination
- Collect urine sample for pregnancy test for females of child bearing potential prior to administration of study medication (where applicable)
- Core set activity measures: physician global activity, patient/parent global activity, manual muscle testing (MMT-8), CMAS, HAQ/CHAQ, MDAAT, muscle enzymes, CHQ PF-50/SF- 36, and Disease activity score (DAS), physician global damage (VAS)
- Dermatology assessment: CDASI, photographs of skin rashes
- Quality of life questionnaires: CHQ PF-50/SF- 36, DLQI, PROMIS/fatigue, and Peds QL fatigue
- Physician and patient/parent assessment of study outcome

- Obtain blood samples for Chem-20, GGT, CK, aldolase, LDH, CBC with diff., von Willebrand Factor antigen level [**may be performed at home institution, up to 10 days before the visit date**]
- Urinalysis
- Collect urine sample for pregnancy test for females of child bearing potential (where applicable)
- Prednisone taper may commence using a predetermined schedule (section 5) if the patient has achieved the Definition of Improvement (DOI) and is rated by the study physician as at least minimally improved.
- Review log of medication self-administration and pharmacy to dispense study medication needed before next visit

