12.0 ADVERSE EVENT REPORTING

12.1 Adverse Events

An adverse event (AE) is any reaction, side effect, or other undesirable or unexpected experience that occurs in conjunction with the use of the study drug, whether or not the experience is considered drug-related. New or worsening signs and symptoms of underlying or emerging disease are also considered adverse events. Adverse events will be tracked through routine communication with the subjects and the family.

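### The before/after adverse event comparison sets chart review against active querying, so for non-serious events it cannot support primary Hypothesis A in either direction

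*Combined protocol and SAP*

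**What the plan says.** Hypothesis A, in Section 2.1, is that abatacept will be tolerated and safe in refractory JDM. The one comparison named for it is this: "Medical records will be reviewed for the 6 months prior to enrollment to obtain adverse events prior to beginning abatacept, which will be compared". The other side of the comparison is every event arising once treatment has begun. The same paragraph asks for particular attention to serious adverse events (SAEs) and infections. Section 3.1 gives no numeric safety criterion.

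Collection on drug is prospective. Section 3.0 sets out "5 protocol visits over six months (week 0, week 6, week 12, week 18, and week 24"), and four of these visits follow the first dose. At each of the four, Section 7.1 tells staff: "Review concomitant medication and query for adverse events and document in CRF". The visits also include an NCI toxicity assessment and laboratory tests. Section 3.2 adds that "in between study visits, a phone call will be made at weeks 2, 4,8,10,14,16, 20 and 22 to review adverse events".

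No section gives the pre-enrolment period a matching interview, a run-in, a person-time denominator or an end date for the on-drug window. Section 12.1 defines an adverse event by its occurrence during use of the study drug, so no definition covers an event before the drug. Section 15 lists adverse event frequencies among its descriptive summaries and assigns no method to the before/after comparison.

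**The concern.** The two periods are measured with different instruments. A mild cold, headache or bout of nausea reaches a chart only if the family mentions it and a clinician writes it down. On drug, the same event is asked about roughly every two weeks. A before/after difference therefore mixes any drug effect with a recording effect, and nothing in the plan separates them.

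Eligibility adds to this for infections, one of the two event types that Hypothesis A singles out. Exclusion 14 ("History of recurrent infection including active skin infections with calcinosis") and the exclusion for recent zoster or herpes simplex thin the pre-enrolment infection count.

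At stake is the reading of one half of the primary objective. An excess on drug could be a recording artefact. The absence of an excess could be an artefact hiding a high pre-treatment event rate.

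**Working it through.** The plan states no adverse event rate, margin or power for this comparison, so there is no figure of its own to reproduce.

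**Inputs from the documents**
- Contacts after the first dose: 4 visits (weeks 6, 12, 18, 24) + 8 phone calls = 12.
- Patients: 10.
- Windows: 6 months before, 6 × 30.44 = 182.6 days; 24 weeks on drug, 24 × 7 = 168 days.
- Event rates from the paediatric JIA study in Section 1.3.2, over 4 months: 70% of patients with any event, 36% with an infection, and 6 SAEs in 190 patients.

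**Assumptions**
- The JIA rates carry over to this population.
- Events are Poisson, with the same true rate in both periods.
- Capture is complete on drug; charts capture a fraction f, taken from 0.9 to 0.3.

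**Step 1: event rates.** Rate per patient-month = −ln(1 − p)/4.
- Any event: −ln(0.30)/4 = 0.301.
- Infection: −ln(0.64)/4 = 0.112.
- SAE, with p = 6/190: 0.008.

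The expected total on drug in 10 patients is 10 × rate × 168/30.44: 16.6 events of any kind, 6.2 infections and 0.44 SAEs. The true pre-enrolment total for any event is 10 × 0.301 × 6 = 18.1, of which charts would show 18.1 × f.

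**Step 2: apparent effect when there is none.** Rate ratio = 1/f. Raw count ratio = (168/182.6)/f = 0.92/f.

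**Step 3: chance that the raw on-drug total exceeds the pre-enrolment total**, computed exactly from two Poisson distributions.

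| f | Rate ratio | Count ratio | Any event | Infections |
|---|---|---|---|---|
| 0.9 | 1.11 | 1.02 | 49% | 46% |
| 0.7 | 1.43 | 1.31 | 74% | 61% |
| 0.5 | 2.00 | 1.84 | 92% | 77% |
| 0.3 | 3.33 | 3.07 | 99% | 91% |

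With equal capture (f = 1) the rate ratio is 1.00. The raw count ratio is then 0.92, and the chance of a higher on-drug total is 37% for any event, so the shorter window works slightly against an excess. Allowing event rates to differ between patients (a shared gamma frailty) changes the any-event figures little: 91% at f = 0.5 and 98% at f = 0.3.

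**Step 4: SAEs.** The chance of an on-drug excess is 25% to 32% across f = 0.9 to 0.3. A tie is the most likely result throughout (50% to 59%).

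**Step 5: if a test is run.** Section 15 can be read as applying a Wilcoxon signed rank test at 0.05 to adverse event counts. Simulating that test with the inputs above gives a significant excess on drug, with no drug effect, in about 2%, 10%, 27% and 57% of trials at f = 0.9, 0.7, 0.5 and 0.3. A valid two-sided 5% test would give at most about 2.5% in that direction (0.05/2), so the test is inflated from f = 0.7 downwards but not at f = 0.9.

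**Step 6: what could cancel the bias.** If the true pre-enrolment rate were 1/f times the on-drug rate, for example 1.43 times at f = 0.7 or 2 times at f = 0.5, the observed rates would be equal.

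**The case against.** A reader might infer that the comparison is bound to show more events on abatacept. The documents do not support that:

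- **Capture is unknown.** No section gives f. At f = 0.9 an excess in the raw total is about a coin flip.
- **SAEs are a different case.** Charts plausibly record them well, and with 0.44 expected on drug a tie is the likeliest outcome. This part stands.
- **Other forces act the other way.** Entry requires refractory, at least moderately active disease, and Section 12.1 counts new or worsening disease signs as adverse events. Refractoriness may also rest on intolerance to earlier agents, which charts should hold if it fell within the 6 months. The pre-enrolment period may therefore be event-rich. This stands too, and it means that the net direction is not established.

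A reader might also infer that a significance test of adverse events is prespecified. That is only one reading of Section 15, which places adverse event frequencies under descriptive statistics and itself doubts the power of any test.

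Two details weaken the contrast a little. Section 12.1 says "Adverse events will be tracked through routine communication with the subjects and the family", which does not describe structured solicitation, and Section 7.1 names the NCI criteria for only four of the eight calls. The screening history and the week 0 toxicity assessment give some pre-drug information beyond charts, though not six months of it.

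Finally, the recording bias on its own works against Hypothesis A, so it would not create a false claim of safety. No decision rule uses the comparison, and safety action rests on related SAEs and DSMB review. This limits the consequence. It does not make the comparison interpretable, because biases of unknown size in opposite directions cannot be assumed to cancel.

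**Conclusion.** The concern holds in a limited form. Section 2.1 prescribes a comparison in which ascertainment differs between the periods, and no section matches or corrects it. For non-serious events it is biased towards an apparent excess on abatacept by about 1/f, or 1.1 to 3.3 for f from 0.9 to 0.3. Selection for active disease may offset this by an unknown amount. The comparison of non-serious events therefore cannot support Hypothesis A, whichever way it comes out.

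The two methods, the 12 contacts and the lack of any matching rule are facts of the text. The size rests on the assumed capture fraction and on JIA event rates carried over to JDM. The claim does not extend to SAEs, for which little bias is expected.

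**What to change.** In Sections 2.1 and 15:

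- Report non-serious events on drug only, as the number of patients affected and the rate per patient-month over a fixed 24-week window, with exact confidence intervals. Make no before/after claim and run no before/after test for them.
- Limit any before/after comparison to SAEs, hospitalisations, and infections that led to a medical visit or prescription treatment. Use one written event definition that applies in both periods, express results per patient-month, and label the comparison descriptive.
- For those event types, count on-drug events from study-site records as well as local records. Local records alone could miss events handled at the study site and tilt the comparison in favour of the drug.

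The cost is a wording change and a request for local records covering the treatment period. Fewer event types are compared, and some difference in sources between the periods remains. Event collection for individual safety monitoring is unchanged.

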patients. Abatacept has been studied in 190 pediatric patients, 6 to 17 years of age, with polyarticular juvenile idiopathic arthritis. Overall frequency of adverse events in the 4-month, lead-in, open-label period of the study was 70%; infections occurred at a frequency of 36%. The most common infections were upper respiratory tract infection and nasopharyngitis. The infections resolved without sequelae, and the types of infections were consistent with those commonly seen in outpatient pediatric populations. Other events that occurred at a prevalence of at least 5% were headache, nausea, diarrhea, cough, pyrexia, and abdominal pain. A total of 6 serious adverse events (acute lymphocytic leukemia, ovarian cyst, varicella infection, disease flare [2], and joint wear) were reported during the initial 4 months of treatment with Abatacept. Of the 190 patients with juvenile idiopathic arthritis treated with abatacept in clinical trials, there was one case of a hypersensitivity reaction (0.5%). During Periods A, B, and C, acute infusion-related reactions occurred at a frequency of 4%, 2%, and 3% respectively, and were consistent with the types of events reported in adults. Upon continued treatment in the open-label extension period, the types of adverse events were similar in frequency and type to those seen in adult patients, except for a single patient diagnosed with multiple sclerosis while on open-label treatment.

Immunogenicity

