4.2 Exclusion Criteria

In order to qualify for participation, subjects must not meet any of the following criteria:

1	Drug-induced myositis (myositis in patients taking medications known to induce myositis-like syndromes, including, but not limited to, statin agents, fibric acid derivatives, and colchicine).
2	Juvenile polymyositis; inclusion body myositis; cancer-associated myositis, defined as the diagnosis of myositis within 2 years of the diagnosis of cancer except basal or squamous cell skin cancer or carcinoma in situ of the cervix if at least 5 years since excision

3	Myositis in overlap with another connective tissue disease (CTD) that precludes the accurate assessment of a treatment response (for example, difficulty in assessing muscle strength in a scleroderma patient with associated myositis)
4	History of receiving a live vaccine 4 weeks prior to initiation of study treatment
5	Does the patient have any of the following concomitant illnesses that would prevent adequate assessments or in the opinion of the investigator pose an added risk to patient: 
 a. Joint disease, severe calcinosis, or other musculoskeletal condition which precludes the ability to quantitate muscle strength b. Wheelchair bound c. Recurrent or chronic infections, including HIV, hepatitis B or C, TB (incl contact with household contact with active TB and no prophylaxis), or recurrent or active infections with calcinosis d. Symptomatic herpes zoster or herpes simplex (not including just simple oral HSV lesions) within past 12 weeks e. Disseminated/complicated herpes zoster (multi-dermatomal involvement, ophthalmic zoster, CNS involvement, post-herpetic neuralgia f. Known liver disease (i.e. cirrhosis or other conditions compromising the synthetic function of the liver) g. Disorder that would preclude accurate assessment of neuromuscular function? h. Cardiomyopathy or arrhythmias that in the investigators opinion poses an additional risk for study participants. i. New York Heart Association Classification III or IV for congestive heart failure. j. Psychiatric illness that precludes compliance or neuromuscular assessment k. Life threatening non-myositis illness that would interfere with the patient's ability to complete the study l. History of cancer within the last 5 years
6	Known hypersensitivity to abatacept or prior receipt of abatacept
7	Serum creatinine > 2.0mg/dl
8	Pregnant females or nursing mothers

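### The before/after safety comparison is filtered by eligibility before enrolment but not after dosing, which biases it towards an apparent rise on abatacept for the event types that entry screens out

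*Combined protocol and SAP*

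**What the plan says.** The primary aim has a safety half, Hypothesis A in Section 2.1. Its only stated comparator is each patient's own recent past: "Medical records will be reviewed for the 6 months prior to enrollment to obtain adverse events prior to beginning abatacept". Events found in those charts are then set against the events seen once treatment has begun. The same paragraph adds: "Particular attention will be given to serious adverse events and infections".

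Section 4.2 decides who can contribute such a past. The relevant exclusions are:

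- 5c: "Recurrent or chronic infections, including HIV, hepatitis B or C, TB"
- 5d: "Symptomatic herpes zoster or herpes simplex (not including just simple oral HSV lesions) within past 12 weeks"
- 5e: disseminated or complicated zoster, with no look-back period
- 12: "Any history or evidence of severe illness or any other condition that would make the patient, in the opinion of the investigator unsuitable"
- 14: "History of recurrent infection including active skin infections with calcinosis"

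The items under exclusion 5 apply where the illness would prevent adequate assessment or, in the investigator's opinion, adds risk. Exclusion 14 carries no such qualifier. *Recurrent* is not defined by a count or a period.

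After dosing, Section 9.0 lists no discontinuation for infection as such and encourages every dosed patient to stay for safety follow-up. Section 15.0 describes adverse event frequencies and promises 95% confidence intervals. It gives no method, denominator or caveat for the before/after comparison.

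**The concern.** A within-patient comparison is informative when the earlier window shows the patient's ordinary risk. Here part of that window has been selected to be free of some of the events the hypothesis singles out. At identical true rates before and after, the screened-out types will on average be more frequent on drug, because only the earlier window was filtered.

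This differs from under-recording. Retrospective chart review against prospective visits and calls may push the same way, but perfect charts would not remove the selection effect.

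At stake is the infection part of a primary safety question in ten patients with no control arm. A rise in these event types could be read as harm when it partly reflects eligibility, and the plan gives the reader no means of separating the two.

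**Working it through.** The plan states no safety rate or calculation to reproduce. The check asks what the contrast would show if abatacept changed nothing.

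**1. Herpes events (exclusion 5d).** Inputs: a 6-month window (365.25/2 = 182.6 days, Section 2.1), a 12-week look-back (84 days, Section 4.2) and 24 weeks on drug (168 days, Section 6.2). Assumptions: constant rate, window ending when eligibility is judged, exclusion always applied.

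- Share of the earlier window blanked: 84/182.6 = 46%.
- Days left that can hold an event: 182.6 − 84 = 98.6.
- Apparent ratio over equal windows: 182.6/98.6 = 1.85.
- Apparent count ratio for 168 days on drug: 168/98.6 = 1.70.

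The wording at the head of exclusion 5 leaves room for judgement, so these are upper bounds.

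**2. All infections, by reading of *recurrent*.** The illustrative rate comes from the juvenile idiopathic arthritis paragraph of Section 1.3.2: "infections occurred at a frequency of 36" per cent in 4 months. Using it for this disease is an assumption. As a Poisson rate, λ = −ln(1 − 0.36) × 6/4 = 0.669 per patient per 6 months. If patients with m or more infections in the window are excluded, the expected earlier count is the Poisson mean truncated below m, while the later mean stays λ:

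- m = 2: λ/(1 + λ) = 0.401; ratio 0.669/0.401 = 1.67.
- m = 3: (λ + λ²)/(1 + λ + λ²/2) = 0.590; ratio 1.13.
- m = 4: (λ + λ² + λ³/2)/(1 + λ + λ²/2 + λ³/6) = 0.652; ratio 1.03.

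If patients differ in their underlying rates (gamma-distributed, shape 2, 1 or 0.5), the ratios become 1.75 to 1.86, 1.22 to 1.33 and 1.07 to 1.17. Without a filter the ratio is 1.00.

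**3. What ten patients would show.** Simulated at the same rate, the chance that the later count exceeds the earlier one is 0.68 to 0.76 (m = 2), 0.53 to 0.58 (m = 3) and 0.46 to 0.52 (m = 4). Unfiltered it is 0.44 to 0.45, ties making up the balance.

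**4. Opposing selection.** Suppose 20% of enrolled patients certainly had an infection in the window because infection made them intolerant of an earlier drug (an assumption).

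- m = 2: the earlier mean becomes 0.8 × 0.401 + 0.2 × 1 = 0.521; ratio 1.29.
- m = 3: patients with one or two infections average (λ + λ²)/(λ + λ²/2) = 1.25, so the earlier mean is 0.8 × 0.590 + 0.2 × 1.25 = 0.722; ratio 0.93.

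The direction for all infections is therefore not fixed.

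**5. Serious infections.** Section 1.3.2 gives 3.0% in adults with rheumatoid arthritis. Taken as 12 months' exposure (an assumption), −ln(0.97)/2 = 0.0152 per patient per 6 months, or 0.15 expected in ten patients. Complete filtering moves the expected count by only 0.15.

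**The case against.** The strongest reply is that most infections are not filtered. A single cold, bronchitis or pneumonia excludes nobody, and Section 1.3.2 names upper respiratory infection and nasopharyngitis as the commonest infections in the paediatric study. If herpes events were 5 to 10% of infections (an assumption), the 46% blank alone would give an all-infection ratio of only 1/(1 − 0.46 × 0.05) = 1.02 to 1/(1 − 0.46 × 0.10) = 1.05. Stable traits such as chronic viral infection leave both windows and create no rise. Much of the filter is discretionary. Safety also rests on toxicity grading, laboratory data, causality assessment, a related-SAE enrolment pause and a monitoring board. No pooled total, test or threshold is planned for the contrast, and a bias against the drug is conservative for safety.

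All of this limits the size of the problem. None of it removes the asymmetry for the screened-out types or supplies the caveat missing from Section 15.0.

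Two stronger readings go too far. A reader might infer that infections as a whole will appear to rise on abatacept. Steps 2 to 4 show that this depends on an undefined word and on the mix of infections, and could be reversed. A reader might also infer that drug toxicity and flare are over-represented before enrolment, biasing those events in the drug's favour. That is possible but not established: inclusion criterion 5 has no 6-month look-back, criterion 6 requires active disease rather than recent worsening, and criteria 7 to 9 require stable doses or washouts, which work against a recent forced change of drug.

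**Conclusion.** The concern holds for a defined set of events: recent symptomatic zoster or non-oral simplex, complicated zoster, recurrent infection, severe illness judged disqualifying, and death. For these, the plan followed as written gives a contrast biased towards a rise on abatacept, and Section 15.0 does not correct or acknowledge it.

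For herpes events the bias is at most about 1.85-fold over equal windows and 1.70-fold in counts against 168 days on drug, assuming a constant rate and strict application of exclusion 5d. For all infections the net bias is probably upward but unknown, from near nil to about 1.9-fold at the borrowed rate of 0.67 per 6 months, and opposing selection could offset it. The 1.85 should not be quoted as the effect on infections generally. The point merits a wording change; it does not undermine the rest of the safety assessment.

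**What to change.** Amend Section 2.1 (Hypothesis A) and Section 15.0 as follows:

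1. Name the screened-out event types, and state how repeated infections are classified for the tables. Do not use the pre-enrolment window as their comparator. Report them on drug only, as n/10 with an exact 95% CI and as events per patient-month.
2. Keep the before/after comparison for other infections and other adverse events, as descriptive person-time rates. Tabulate infections, disease worsening, drug intolerance and other events separately, with no pooled total. State the eligibility filtering as a limitation.
3. If the 36% (infections) and 70% (any adverse event) over 4 months from Section 1.3.2 are shown, set them beside the all-infection and any-event figures on drug over the same duration, labelled as external figures from another disease. They should not stand beside the screened-out types alone, because they cover all events of their kind.

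This needs no new data. The cost is losing the within-patient contrast for a few event types, and the on-drug figures that replace it will be imprecise: with 0 of 10 patients affected, the exact upper limit is 1 − 0.025^(1/10) = 31%.
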